8.2.5.4. Response to sunitinib treatment

Analysis population: FAS population

Analysis:

The response to treatment will be assessed by the investigator based on RECIST v1.1 criteria (complete response, partial response, stable disease or progression) and will be described at each follow-up time (at the end of cycles 1, 2 and 4) (cf. section 8.2.3. Description of patients during the follow-up period).

The best response obtained during treatment with sunitinib will be identified from the responses assessed according to RECIST v1.1 criteria. “Unevaluable” responses will not be included in the definition of the best response.

The proportion of patients with a complete or partial best response during the follow-up period (objective response rate) will be estimated.

The last response assessed during the study will also be estimated.

The analysis will be performed on an overall basis and by the number of calls made by the call center.

Analysis of response will also be assessed on the FAS population imputing missing data points by failure (= progression).

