Emphasis shall be placed on the quality of these contacts as they shall promote the involvement and quality of work performed by the participating physicians. Each physician shall, insofar as possible, be monitored by the same research associate, from enrolment to closure of the study.

The research associates shall follow up on incomplete or incoherent data (incoherence, lack of response and omission checks) and shall maintain constant contact with the participating physicians. During the patient selection period and depending on the number of inactive participating physicians (no patient selected), the research associates may be required to make follow-up calls to these latter.

Moreover, a study-specific freephone number shall be set up for the participating physicians, in order to immediately answer any queries they may have throughout the duration of the study.

In terms of traceability, all "incoming" calls via the freephone number and "outgoing" calls (selection call, follow-up call, etc.) will give rise to a written report (date, purpose of the call, steps to take, etc.) and will be entered into a log.

Receipt and input of satisfaction and compliance questionnaires

The compliance and satisfaction questionnaires completed by the patients will be sent directly to Pfizer by means of postage-paid envelopes provided to the participating physicians.

After acknowledging receipt, Pfizer sends them in batches to the CRO in charge of data input, where they are entered in duplicate into the database.

Call management

The nurse in charge of patient follow-up via the "therapy management platform", upon receipt of the contact sheet, will enter the patient's contact details into the CATI system. An call identification number (IDcall) will be assigned to the patient. This database will be secure and accessible via login and password to persons in charge of making the calls from the platform. When recording the patient's file, these data will be encrypted in the database. It will subsequently be impossible to access the complete IDstudy / IDcall / patient details chain.

Calls will then be performed according to intervention procedures (Appendix 8) defined for the patients.

End of study

A patient leaves the study in one of the following cases:

- once all 4 treatment cycles have been completed.
- when the patient stops his/her treatment with sunitinib, for whatever reason.

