8.5. Complete population justification (physicians/patients)

The patients included in this study will receive support from a therapy management platform in addition to usual follow-up by their oncologist.

The estimated number of patients (n) is determined by the precision (i) required when estimating the proportion (p) of patients presenting with at least one grade 3 or 4 AE. A 95% confidence interval is associated with the estimation of this proportion. The smaller the amplitude of this confidence interval, the greater the precision. Precision is given by the following formula:

$$i = 1.96 \sqrt{\frac{p(1-p)}{n}}$$

Depending on the observed proportion and on the size of the studied population, the following precision levels may be achieved:

Observed proportion	Resulting precision		
	n=75	n=100	n=125
10 – 90	6.8	5.9	5.3
20 – 80	9.1	7.8	7.0
30 – 70	10.4	9.0	8.0
40 – 60	11.1	9.6	8.6
50	11.3	9.8	8.8

Precision is minimum where the amplitude of the maximum confidence interval for a given proportion is equal to 50%. Failing any hypothesis concerning the value of the expected proportion, the hypothesis of a 50% proportion will be used. Thus, we can show that 100 patients will need to be included to estimate a percentage with a 95% confidence interval whose amplitude does not exclude $\pm 9.8\%$.

Between 10 and 20 centres are expected to participate in France, that shall each include 10 patients on average.

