5. ANALYSIS POPULATION

5.1. *Definition of the analysis populations*

Reported population	All patients reported by the investigators in the non-inclusion register and included in the eCRF.
Safety population	Patients treated with Sunitinib.
Full Analysis Set (FAS) Population	All patients included by the investigating doctors who meet the study eligibility criteria and have received at least one dose of Sunitinib

NB: Where applicable, the two subgroups of patients will in all cases be distinguished in the populations: firstly patients included in the “Call Center” arm (**main interest population**) and patients included in the “standard follow-up” arm (**exploratory population**) set up as part of the initial study design (before amendment No. 3 to the protocol).

Table 3: Population in each analysis

Analyses		Populations analyzed	Analysis subgroup*
Description at inclusion		Safety population	Call Center /standard follow-up
Description of follow-up	All data Main data	Safety population Call Center Safety population Standard follow-up	
Primary objective		Safety population	Number of calls made by the call center*
Secondary objectives	Sunitinib treatment details Planned and unplanned medical procedures Adherence to treatment Objective response rate Telephone calls	Safety population Safety population Safety population FAS population Call Center FAS population	Number of calls made by the call center* Number of calls made by the call center* Number of calls made by the call center* Number of calls made by the call center*
	Patient satisfaction Doctor satisfaction	Call Center FAS population who completed a self-administered satisfaction questionnaire Call Center FAS population for which the Doctors have completed a satisfaction questionnaire	Number of calls made by the call center*
Pharmacovigilance		Safety population	

* cf. definition §5.2.

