9.5.4. Response to the sunitinib treatment

Table 44: Response to sunitinib treatment (FAS population)

		Number of calls received < xx (N=xxx)	Number of calls received ≥ xx (N=xxx)	Call center (N=xxx)
Best response obtained during treatment according to RECIST v1.1 criteria	CR (Complete response)	xx (xx%)	xx (xx%)	xx (xx%)
	PR (Partial response)	xx (xx%)	xx (xx%)	xx (xx%)
	SD (Stable disease)	xx (xx%)	xx (xx%)	xx (xx%)
	PD (Progressive disease)	xx (xx%)	xx (xx%)	xx (xx%)
Missing value				
Best complete or partial response (Objective response rate)	Yes	xx (xx%)	xx (xx%)	xx (xx%)
	No	xx (xx%)	xx (xx%)	xx (xx%)
	Missing value	xx -	xx -	xx -

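### The row labelled objective response rate is a rate among evaluable patients, not the FAS, and the additional analysis overstates progression in the best-response table

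*SAP*

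**What the plan says.** - **Population.** SAP 8.2.5.4 assigns response to the FAS. SAP 5.1 defines the FAS as "All patients included by the investigating doctors who meet the study eligibility criteria and have received at least one dose of Sunitinib". No tumour assessment is needed to belong to it.
- **Best response.** SAP 8.2.5.4 derives best response from the RECIST assessments and states that unevaluable "responses will not be included in the definition of the best response". It defines the ORR as the proportion with CR or PR as best response, without naming a denominator.
- **Missing data.** SAP 7 makes observed-case analysis the default and takes missingness to carry no information.
- **Table shell.** In Table 44 (SAP 9.5.4) the block "Best complete or partial response (Objective response rate)" has Yes and No with percentages, and a missing-value line with a count and a dash. The best-response block lists CR, PR, SD, PD and missing, with no not-evaluable category. Table 60 (SAP 9.7.5) repeats this layout for standard follow-up.
- **Additional analysis.** SAP 8.2.5.4 adds: "Analysis of response will also be assessed on the FAS population imputing missing data points by failure (= progression). SAP 7 says the same. No separate shell is given for it.
- **Leaving the study.** Under Protocol 8.2, one way a patient leaves is "when the patient stops his/her treatment with sunitinib, for whatever reason". The same list is followed by an exit visit and an end-of-treatment form. That form (Protocol Appendix 6, form section 4) records best RECIST response, with a not-assessable option and a reason.

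**The concern.** A row titled ORR in a table titled FAS will be read as responders over the FAS. As the plan stands, it is responders over those FAS patients who have an evaluable response. If lack of an evaluable response is related to outcome, the row describes a selected group.

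That is possible here. Patients leave when sunitinib stops, the first follow-up visit is at about week 6, and progression, toxicity and death are among the stopping reasons on the end-of-treatment form. The non-informative assumption in SAP 7 is therefore not obviously safe for this endpoint.

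The additional analysis brings these patients back, but under the label of progression. One version leaves them out of the best-response percentages and the other counts them as PD, so neither gives a correct best-response distribution over the FAS.

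**Working it through.** **1. The plan's own figure.** The only sizing figure is for the grade 3 or 4 AE proportion (Protocol 8.5): "100 patients will need to be included to estimate a percentage with a 95% confidence interval", and "the hypothesis of a 50% proportion will be used". The half-width is 1.96 × √(0.5 × 0.5 / 100) = 0.098, so the stated ±9.8 points reproduces. At 30% the same formula gives 1.96 × √(0.3 × 0.7 / 100) = 0.090, as in the protocol's precision table. Nothing is sized for the ORR.

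**2. Who is in the denominator.** The best-response sentence alone removes nobody who has another evaluable visit. The exclusion needs three provisions together:
- a patient with only unevaluable assessments, or none, has no best response (SAP 8.2.5.4);
- patients without a value are not analysed (SAP 7);
- the missing line carries no percentage (Table 44).

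Reading the dash as outside the denominator is an inference, but it fits the other shells. Table 24 prints a percentage for not evaluable at each visit, and Table 11 prints one for an unavailable Heng score.

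**3. Effect on the ORR.** Let N be the FAS size, r the responders and m the patients with no evaluable response.
- All-FAS ORR = r / N
- Table 44 ORR = r / (N − m) = (r / N) × 1 / (1 − m / N)

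Take N = 100, the planned number, assuming all are eligible and dosed. The values of r and m are assumptions.

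| m | r = 20 | r = 30 | r = 40 | ratio to r/N |
|---|---|---|---|---|
| 5 | 21.1% | 31.6% | 42.1% | 1.05 |
| 10 | 22.2% | 33.3% | 44.4% | 1.11 |
| 20 | 25.0% | 37.5% | 50.0% | 1.25 |
| 30 | 28.6% | 42.9% | 57.1% | 1.43 |

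The excess runs from 1.1 points (r = 20, m = 5) to 17.1 points (r = 40, m = 30).

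**4. Effect of the additional analysis.** If not evaluable counts as missing, the imputed ORR is r / N. Suppose instead that it does not, and that u of the m patients have only unevaluable assessments and stay excluded. The imputed ORR is then r / (N − u). With r = 30, m = 20 and u = 10, it is 30 / 90 = 33.3%. The SAP does not say which applies.

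For PD, assume 20 observed progressions per 100 and m = 20:
- observed case: 20 / 80 = 25%
- missing coded as progression: (20 + 20) / 100 = 40%
- separate not-evaluable row: 20 / 100 = 20%

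**The case against.** The strongest reply is that the all-patients ORR is already planned, in both SAP 7 and SAP 8.2.5.4. Calling a missing patient a progressor rather than a non-responder cannot change the ORR. This stands, provided not evaluable counts as missing. For the ORR, the change is then mainly one of which figure carries the label and of stating its denominator.

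The missing count is also printed, so a reader of Table 44 can recover r / N. Table 24 and Table 56 report not-evaluable assessments by visit. ORR is one of several secondary objectives in a descriptive analysis without tests. With r = 30 and 5% to 10% missing, the shift of 1.6 to 3.3 points is smaller than the ±9.0 points of sampling error at 30%. All of this limits the consequences. It does not make the label right, and sampling error does not excuse a known upward difference.

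A reader might infer that the patients left out are mainly early stoppers or early failures. The documents do not support that. There is an exit visit, and the end-of-treatment form captures best response. Tumour evaluation is a yes/no item at each visit (Protocol Appendix 6, form section 3.1), so a patient still on treatment may also lack a scan. If some are missing for unrelated reasons, r / N is itself too low for the underlying response rate.

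**Conclusion.** The point holds as a matter of definition and reporting. The only row labelled ORR for the call-centre group has evaluable patients as its denominator, although the table names the FAS. It is never below the all-FAS rate, and exceeds it once there is at least one responder and one patient without an evaluable response. The direction is arithmetic. The size is not known: against 30.0%, the row reads 31.6% at 5% missing, 33.3% at 10% and 37.5% at 20%, and both the response rate and the missing share are assumed.

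The fault in the additional analysis lies mainly in the category table, where PD is overstated. Its ORR is the all-FAS rate if the unstated rule on not-evaluable patients goes that way.

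It would be too strong to say that the trial's headline ORR is inflated. The documents do not say which ORR will be quoted, and they do not say who will be missing.

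**What to change.** - In SAP 8.2.5.4, define the ORR as CR+PR over all patients of the analysis population, with not evaluable or not assessed counted as non-response.
- In SAP 7 and 8.2.5.4, replace the coding of missing response as progression with *non-responder*, and state that not evaluable is treated the same way.
- Add a row *Not evaluable / not assessed*, with a percentage, to best response in Tables 44 and 60.
- Keep the evaluable-only rate as a secondary line, named as such.

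The cost is SAP wording and one row in each table. No new data are needed, since the visit form and the end-of-treatment form already have a not-assessable option with a reason. The downside is a slightly lower labelled ORR, which is conservative if some patients lack a scan for unrelated reasons. The secondary line covers that case.

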8.2.5.5. Telephone calls made

Analysis population:

- FAS population, regardless of the number of calls completed.
- All calls made.

Analysis:

The average number of planned, unplanned and the total number of calls made per patient will be presented on an overall basis and by treatment cycle.

The conduct of the telephone calls will be described using the following indicators:

- **Action taken by the patient;**
- **And/or action taken by the doctor;**
- **Declaration of adverse events;**
- **Action taken by the call center.**

8.2.5.6. Doctor satisfaction with the call center

Analysis population: FAS population for which the Doctors have completed a satisfaction questionnaire

Analysis:

The doctor's satisfaction with the call center will be assessed from the doctor satisfaction questionnaire which will be completed by the doctors at the end of the follow-up period.

This questionnaire, which has been constructed for the study, is made up of 5 questions with responses in the form of a semantic odd number measurement scale (5 modalities: "Very unsatisfied", "satisfied", "not particularly satisfied", "unsatisfied" and "no opinion"), including 3 satisfaction dimensions (overall satisfaction, satisfaction with the advice given and satisfaction with the management).

Each response is allocated a positive or negative score (+2, +1, -1, -2 and no score) respectively allowing a quantitative score to be established for each item. A score will be calculated for each dimension of the questionnaire by calculating the mean scores obtained for each item if at least 50% of the items for the dimension have been completed (and are not "no opinion").

The doctor's satisfaction with the call center will be assessed from:

- **The mean score for each dimension:** A radar plot with 3 axes will be proposed in order to simultaneously show the mean scores for each dimension. In this type of display, the mean scores are linked together and form a polygon. The area of the polygon will be described and the ratio between the area of the polygon and the ratio of the ideal polygon (complete coverage of the radar plot) will be used to assess the percentage surface area covered. A high area represents better general satisfaction.
- **The proportion of doctors who reported themselves as being "Very satisfied" or "Satisfied" overall with management by the call center (5th item of the questionnaire).**

These doctors will be described by sex, age and number of patients in the CC arm before being involved with the call center when at least 50% of the planned calls are completed.

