8.2.5.7. Patient satisfaction with the call center

Analysis population: FAS population included in the Call Center arm who completed a self-administered satisfaction questionnaire.

Analysis:

The patient satisfaction analysis with the call center will be assessed from the self-administered satisfaction questionnaire completed at the end of the study by each patient in the CC arm. This questionnaire together with the doctor questionnaire has been created for this study.

The questionnaire contains 8 items, and is theoretically completed during the final visit at week 6 of cycle 4. For patients who stop their treatment at the end of cycles 1, 2 or 3, the questionnaire will be completed in the last follow-up visit performed (the visit in which discontinuation of treatment is notified).

Definition of scores by dimension (overall satisfaction with advice, satisfaction with the service and satisfaction with the management) will be similar to what is described in the previous section “doctor satisfaction with the call center”.

Patient satisfaction with the call center will be assessed from:

- **The mean scores for each dimension;** a radar plot with 4 axes will be proposed in order to simultaneously represent the mean scores for each dimension. In the same manner as for the assessment of doctor's satisfaction, the area of the polygon and percentage of subjects covered will be described.
- **The proportion of patients who reported themselves as being “Very satisfied” or “Satisfied”** overall with the support offered by the call center (8th item of the questionnaire).

These patients will be described by their major characteristics when they started sunitinib (sex, age, ECOG score, etc.).

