9.5.6. Satisfaction with the call center

9.5.6.1. Doctors' satisfaction with the call center

Table 49: Satisfaction of doctors who included patients followed up by the call center with the patient treatment management call center

		Doctors who included at least 1 patient into the Call Center arm (N=xxx)
Satisfaction assessed at the end of the patient follow-up period		
Satisfaction with the advice		
- In terms of the reduction in the number and/or frequency of grade 3/4 AEs as a result of the advice delivered during the support process	Very satisfied Satisfied Not particularly satisfied Not satisfied No opinion	xx (xx%) xx (xx%) xx (xx%) xx (xx%) xx (xx%)
- With the improvement in adherence to treatment through the support	Very satisfied Satisfied Not particularly satisfied Not satisfied No opinion	xx (xx%) xx (xx%) xx (xx%) xx (xx%) xx (xx%)
- With the change in patient's quality of life through the advice delivered by the call center	Very satisfied Satisfied Not particularly satisfied Not satisfied No opinion	xx (xx%) xx (xx%) xx (xx%) xx (xx%) xx (xx%)
Satisfaction with care		
- Feeling that the treatment management call center care reduced workload	Very satisfied Satisfied Not particularly satisfied Not satisfied No opinion	xx (xx%) xx (xx%) xx (xx%) xx (xx%) xx (xx%)
Overall satisfaction of patient care with the call center		
	Very satisfied Satisfied Not particularly satisfied Not satisfied No opinion	xx (xx%) xx (xx%) xx (xx%) xx (xx%) xx (xx%)
Overall satisfaction: Doctor "satisfied" or "very satisfied"	Yes No	xx (xx%) xx (xx%)
Desire to continue this type of support	Yes No	xx (xx%) xx (xx%)

A 3 axis radar plot shows the mean satisfaction scores for each dimension. The area of the polygon and percentage surface area covered are shown on the plot. A high represents greater general satisfaction.

Table 50: Characteristics of doctors who were satisfied or very satisfied with the support from the patient treatment management call center

		Overall satisfied or very satisfied with the support	
		Yes (N=xxx)	No (N=xxx)
Age of doctor	Number analyzed	xxx	xxx
	Mean (\pm SD)	xx (\pm xx)	xx (\pm xx)
	Median	xx	xx
	Min-Max	xx - xx	xx - xx
Sex	Male	xx (xx%)	xx (xx%)
	Female	xx (xx%)	xx (xx%)
Number of patients who used the call center for at least 50% of the planned calls	Number analyzed	xxx	xxx
	Mean (\pm SD)	xx (\pm xx)	xx (\pm xx)
	Median	xx	xx
	Min-Max	xx - xx	xx - xx

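### The radar-plot area is read as general satisfaction but does not track the mean scores, has no stated centre and, for patients, depends on an unstated axis order (minor)

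*SAP*

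**What the plan says.** SAP 8.2.5.6 (doctors) scores the items as follows: "Each response is allocated a positive or negative score (+2, +1, -1, -2 and no score) respectively". Items are averaged within a dimension, so dimension scores run from -2 to +2. For display, "A radar plot with 3 axes will be proposed in order to simultaneously show the mean scores for each dimension". The polygon's area is described, and its ratio to the ideal polygon "will be used to assess the percentage surface area covered". The reading rule is "A high area represents better general satisfaction".

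SAP 8.2.5.7 (patients) follows the same approach: "a radar plot with 4 axes will be proposed in order to simultaneously represent the mean scores for each dimension", and "the area of the polygon and percentage of subjects covered will be described". The notes under Tables 49 and 51 (SAP 9.5.6.1 and 9.5.6.2) repeat the area, the percentage of surface covered and the reading rule. Neither section states the value at the centre of the axes or the order of the dimensions around the plot.

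SAP 6.2 defines the satisfaction end points as the mean score for each dimension and the proportion satisfied or very satisfied overall. Tables 49 and 51 have rows for the item frequencies and for that proportion, but none for the dimension means, which appear only on the plot.

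On labels, SAP 8.2.5.6 lists the responses as "5 modalities: 'Very unsatisfied', 'satisfied', 'not particularly satisfied', 'unsatisfied' and 'no opinion", while Table 49 has "Very satisfied Satisfied Not particularly satisfied Not satisfied No opinion".

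**The concern.** Satisfaction with the call center is a secondary objective. The area and percentage covered are the only numbers that combine the dimensions, and they come with an instruction on how to read them. A reader of the report would take a larger percentage as more satisfaction. If the percentage can stay the same while the mean scores differ, or change when the axes are rearranged, that reading is not safe. Without a stated centre, the percentage cannot be reproduced from the SAP at all.

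**Working it through.** The SAP gives no numerical value for the area, so there is no figure to reproduce. The score profiles below are illustrations.

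**Inputs.** Dimension scores s from -2 to +2; k = 3 axes for doctors (SAP 8.2.5.6) and k = 4 for patients (SAP 8.2.5.7).

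**Formula.** For k equally spaced axes with radii r scaled so that the maximum is 1, area = ½·sin(2π/k)·Σ rᵢrᵢ₊₁, with the last axis next to the first. The ideal polygon has every r = 1, so coverage = (1/k)·Σ rᵢrᵢ₊₁. With centre -2, r = (s + 2)/4. With centre 0, r = s/2.

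**1. Different means, same area (3 axes, centre -2).**
- (0, 0, 0): r = 0.5 each; coverage = (0.25 + 0.25 + 0.25)/3 = 25%. Mean 0.
- (2, 1, -2): r = 1, 0.75, 0; coverage = (0.75 + 0 + 0)/3 = 25%. Mean (2 + 1 - 2)/3 = +0.33.

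The converse also occurs. (0, 0, 0), (1, 0, -1) and (2, 0, -2) all have mean 0 but cover 25.0%, 22.9% and 16.7%.

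**2. Curvature (centre -2, all dimensions equal).** Coverage is ((s + 2)/4)². All neutral gives 25% and all +1 gives 56.25%, where a linear index (s + 2)/4 gives 50% and 75%.

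**3. Axis order.**
- Three axes: every pair is adjacent, so coverage = (r₁r₂ + r₂r₃ + r₃r₁)/3 in any order. The doctor plot has no order effect.
- Four axes: coverage = (r₁ + r₃)(r₂ + r₄)/4, which depends on which dimensions face each other. For (2, 2, -1, -1) with centre -2, r = 1, 1, 0.25, 0.25. With the two high scores adjacent, coverage is 1.25 × 1.25/4 = 39%. With the high scores opposite each other, it is 2 × 0.5/4 = 25%, the value for four neutral scores.
- When the dimensions differ less, the effect is small: (1.5, 1, 0.5, 0) gives 45.7%, 46.9% or 47.3% according to order, a spread of 1.6 points.

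**4. Centre.**

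| All dimensions at | Centre 0, signed scores | Centre -2 |
|---|---|---|
| -1 | (-0.5)² = 25% | 0.25² = 6.25% |
| +1 | 0.5² = 25% | 0.75² = 56.25% |

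The equality of -1 and +1 arises only if signed scores are plotted from 0.

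**The case against.** The strongest reply is that the area decides nothing. The end points in SAP 6.2 are the dimension means and the proportion satisfied. Overall satisfaction has its own questionnaire item, SAP section 4 has no tests or decision rules, and SAP 8.1.1 calls the analysis purely descriptive. Any area is quadratic, and with centre -2 raising one dimension never lowers it. All of this stands and keeps the point minor. It does not rescue the reading rule, which is stated without qualification and fails even with centre -2.

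Three stronger readings are tempting, and the documents do not support them.

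- **That the index scores dissatisfaction like satisfaction.** This needs signed scores plotted from 0. The SAP states no centre, and its description of the ideal polygon as full coverage fits a scale starting at -2 at least as well. The supported finding is that the centre is unspecified.
- **That axis order affects both questionnaires.** It affects only the four-axis patient plot.
- **That scoring is reversed, with +2 for the worst answer.** Taken literally, the label list in SAP 8.2.5.6 pairs +2 with very unsatisfied. The same section's definition of a satisfied doctor, Tables 49 and 51, and Protocol Appendices 10 and 11 all have very satisfied as the top category. This is a wording slip, not a scoring plan.

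It can also be said that stating the centre and the patient axis order would be enough. That would make the number reproducible, but steps 1 and 2 of the working would remain.

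**Conclusion.** The point holds as a minor one. The area and percentage covered do not reliably track the mean scores for either questionnaire. For patients they also depend on an axis order that the SAP leaves open, and for both the centre is unstated. The illustrations show a mean of +0.33 covering the same 25% as all-neutral scores, and a swing between 39% and 25% from axis order alone. These use widely separated dimension scores; with closer scores the order effect can be below 2 points. The figures for means and order assume centre -2, the more favourable choice for the SAP. No end point, test or decision is affected. What could mislead is one published percentage and the sentence that interprets it. A related gap is that the tables have no row for the dimension means, although these are a defined end point.

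**What to change.** - In SAP 8.2.5.6, 8.2.5.7 and the notes to Tables 49 and 51, delete the polygon area, the percentage covered and the sentence interpreting them. Keep the radar plot as a picture, with the centre stated as -2.
- Add rows to Tables 49 and 51 for the mean of each dimension with SD and 95% CI, and add a 95% CI to the proportion satisfied or very satisfied. This matches Protocol 7.3.2, which provides for mean and standard deviation of these scores, and Protocol 8.7.2, which calls for confidence intervals.
- In SAP 8.2.5.6, correct the first response label so that +2 belongs to very satisfied.
- In SAP 8.2.5.7, the reference to a percentage of subjects covered should have meant surface area, as the note to Table 51 shows; remove it with the area.

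The cost is one descriptive output removed, a few table rows added and one label corrected. Data collection does not change.
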